Procedure	Screening ≤ 6 Weeks prior to Randomization	Randomize Initiate study drug (Day 1) within 72 hours	On Study Treatment Weeks 4, 8, 12 ± 3 days, and every 12 weeks ± 5 days up to end of study drug dosing	Weeks 52, 100 and 148 ± 10 days (if needed) ^a	End of Treatment (Scheduled or Early)	Observational LTFU ^b Weeks 6, 12, and every 12 weeks ± 5 days Up to 264 weeks total study participation [or 48 weeks beyond completion of rescue open- label ETV used for treatment of an extreme elevation of ALT due to acute exacerbation of CHB; whichever is later]	Protocol Section
Specimens for Resistance Testing (3 mL)		X	Week 48, 96, 144 ^j		X		6.9
Other Assessments							
Sparse PK (2 ml) ^k			Weeks 4, 12, 24, 48				
Semi-intensive PK (8 ml) ^l			Week 4				
Clinical Drug Supplies							
Dispense Study Medication		X	X	X		X ^d	5.2
Assessment of Study Medication Use			X	X	X	X ^d	5.6

- ^a Assessments of seroconversion will be made based on serology results at Weeks 48, 96, and 144. Study drug will be modified, continued, or discontinued according to the study schema (Section 4.1).
- ^b Only protocol required visits and assessments are mentioned. Subjects placed on rescue open-label ETV to treat an extreme elevation of ALT due to acute exacerbation of CHB should undergo additional non-protocol visits and assessments at investigator discretion.
- ^c Histological results will be documented for subjects who have had a prior liver biopsy.
- ^d For subjects receiving rescue open-label ETV to treat an extreme elevation of ALT due to acute exacerbation of CHB only.
- ^e Adverse events should be recorded at week 6 for all subjects enrolled in LTFU, and at each visit for subjects receiving rescue open-label ETV.
- ^f Volume of blood to be collected may vary based on available specimen collection tubes.
- ^g While on study treatment.
- ^h WOCBP only. Additional home pregnancy testing will be required in between study visits starting from Week 18 and every 12 weeks thereafter while on study treatment.
- ⁱ All subjects enrolled in LTFU should undergo pregnancy testing at week 6. Subjects receiving rescue open-label ETV should be tested every 6 weeks during treatment and 6 weeks after the last dose of study medication (home pregnancy tests should be used in between study visits).
- ^j For subjects still on study ETV only (Section 6.9.2).

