6.3.2 Adverse Event Monitoring

Subjects will be closely monitored throughout the study for adverse events. Subjects who have study medication completed or discontinued permanently must be followed for the full 5 years of the study.

During the dosing phase, palatability issues with respect to the oral solution (placebo or active drug) should be reported as Adverse Events.

During the observational long-term follow up phase, Adverse Events related to the administration or discontinuation of study drug should be documented for subjects that are not receiving commercially available anti-HBV therapy. Serious Adverse Events and HBV-related diagnoses should be reported during the long-term follow up phase, regardless of whether or not the subjects are receiving commercially available anti-HBV therapy.

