7.3.3 Nonserious Adverse Events

The collection of nonserious AE information should begin at initiation of study drug. Nonserious AE information should also be collected from the start of a placebo lead-in period or other observational period intended to establish a baseline status for the subjects. During the long-term follow up phase, Adverse Events related to the administration or discontinuation of study drug should be documented for subjects that are not receiving commercially available anti-HBV therapy. Also during the LTFU phase, all adverse events should be documented in subjects receiving rescue open-label ETV.

If an ongoing nonserious AE worsens in its intensity or its relationship to the study drug changes, a new nonserious AE entry for the event should be completed. Nonserious AEs should be followed to resolution or stabilization, or reported as SAEs if they become serious (see Section 7.3.1). Follow-up is also required for nonserious AEs that cause interruption or discontinuation of study drug, or those that are present at the end of study treatment as appropriate.

All identified nonserious AEs must be recorded and described on the appropriate nonserious AE page of the CRF (paper or electronic).

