## 6 STUDY PERIODS, TREATMENT REGIMENS AND POPULATIONS FOR ANALYSES

### 6.1 Study Periods

Study periods for efficacy and safety analyses are defined as follows:

- **Pre-treatment period** begins at the first visit until initiation of study therapy.
- **On-treatment period** begins after the first day of study therapy and ends at the last dose of study therapy plus 5 days.
- **ETV treatment period** begins after the first day of active ETV and ends at the last dose of active ETV plus 5 days.
- **Off-treatment follow-up period** begins on the last dose of study therapy plus 6 days and ends at the start of alternative anti-HBV therapy minus 1 day.
- **Long-term follow-up period** begins on the last dose of study therapy plus 6 days until the end of the study.
- **Alternative ETV follow-up period** begins on the later of the last dose of study therapy plus 6 days and the start of alternative ETV therapy, until the end of the study.

Note that rescue open-label ETV is considered alternative anti-HBV therapy. See [Section 8.9](#) for additional conventions.

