### 7.6.5 Overall Adverse Events

AEs are summarized by intensity (All Grades; All Grades related; Grade 2 - 4 related; Grade 3 - 4) and treatment regimen for the following 3 cohorts:

- Through Week 48 on blinded therapy for treated subjects
- After Week 48 on blinded therapy or on open-label ETV through Week 96 for the Year 2 Safety Cohort
- On ETV treatment for the All ETV Safety Cohort

If relationship to study therapy is missing, the AE is included in summaries of AEs related to study therapy.

AEs are also summarized by intensity (All Grades) and treatment regimen during (1) off-treatment follow-up for off-treatment follow-up subjects in the Post-Year 1 Safety Cohort, (2) alternative ETV follow-up for alternative ETV follow-up subjects in the Post-Year 1 Safety Cohort, and (3) long-term follow-up for long-term follow-up subjects in the Post-Year 1 Safety Cohort.

On-treatment non-serious AEs (All Grades) occurring with incidence  $\geq 5\%$  on any treatment regimen are also summarized analogously for the 3 cohorts. Multiple on-treatment non-SAEs (All Grades) occurring with incidence  $\geq 5\%$  on any treatment regimen are also summarized for the 3 cohorts, presenting the numbers of events and exposure-adjusted incidence rates (see [Section 8.10](#)).

Multiple on-treatment AEs (All Grades) occurring with incidence  $\geq 5\%$  on any treatment regimen are also summarized for the 3 cohorts, presenting the numbers of events and exposure-adjusted incidence rates (see [Section 8.10](#)).

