- Dose end date of active ETV is the dose end date of study therapy for ETV-randomized subjects and the dose end date of open-label ETV for PBO-randomized subjects. This date is used to assess time on active ETV.
- Last dose date of active ETV is the dose end date of active ETV derived only when the last dose date of study therapy is not missing.
- Start date of rescue open-label ETV is the earliest start date of rescue open-label ETV identified from valid dosing records, ie, non-missing start date and total dose > 0, from rescue open-label ETV study medication CRFs.
- Start date of alternative ETV therapy is the earliest start date of (1) rescue open-label ETV, or (2) concomitant ETV taken on treatment or during long-term follow-up.
- Start date of alternative anti-HBV therapy is the earliest start date of (1) rescue open-label ETV, or (2) concomitant anti-HBV medication taken on treatment or during long-term follow-up.
- Last contact date is the death date, if it exists, or the latest of the following dates: randomization; first or last dose of study therapy; adverse event onset or resolution; hepatitis B related diagnosis; laboratory test (safety, pregnancy, serology and virology); liver biopsy; physical measurement; physical exam; neurologic exam; vital sign; non-study medication start or stop; last contact from end of treatment or end of study subject status; Tanner staging.

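### The alternative-ETV follow-up AE table pools rescue users, who have full AE collection, with commercial ETV users, who have little beyond SAEs, so it understates incidence; the long-term table mixes three collection rules

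*SAP*

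**What the plan says.** **Analysis.** SAP 7.6.5 defines three follow-up AE tables, numbered here as the SAP numbers them. It opens with "AEs are also summarized by intensity (All Grades) and treatment regimen during (1) off-treatment follow-up" and goes on to "2) alternative ETV follow-up for alternative ETV follow-up subjects in the Post-Year 1 Safety Cohort, and (3) long-term follow-up for long-term follow-up subjects". No follow-up table is split by relationship to drug or by source of ETV. SAP 7.6 makes AE presentations cover serious and non-serious events together unless stated otherwise.

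**Who is in table (2).** SAP 8.9 starts alternative ETV at "the earliest start date of (1) rescue open-label ETV, or (2) concomitant ETV taken on treatment or during long-term follow-up". SAP 6.3 admits a child with one dose of it and one assessment in the period; a laboratory date is enough. SAP 6.1 opens the period at the later of the last study dose "plus 6 days and the start of alternative ETV therapy, until the end of the study".

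**Collection.** The protocol varies AE collection in long-term follow-up (LTFU) by therapy:
- Rescue ETV (Protocol 7.3.3): "Also during the LTFU phase, all adverse events should be documented in subjects receiving rescue open-label ETV".
- No commercial therapy (Protocol 6.3.2): "Adverse Events related to the administration or discontinuation of study drug should be documented for subjects that are not receiving commercially available anti-HBV therapy".
- Everyone (Protocol 6.3.2): "Serious Adverse Events and HBV-related diagnoses should be reported during the long-term follow up phase, regardless of whether or not the subjects are receiving" commercial anti-HBV therapy.
- Schedule (Protocol Table 6.1, footnote e): "Adverse events should be recorded at week 6 for all subjects enrolled in LTFU, and at each visit for subjects receiving rescue open-label ETV".

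**The concern.** An AE percentage is an incidence only if every child in the denominator was observed for the events in the numerator. In table (2), a commercial ETV user counts fully below the line but has almost no route for a non-serious AE to appear above it. Table (2) is the planned AE summary for children who restart ETV after study therapy, and long-term paediatric safety is a stated secondary objective. A reader would take its percentage as the AE experience after restart, when it partly reflects how the drug was supplied. The error runs towards reassurance.

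Commercial supply is an expected route. Protocol 4.1.1 allows marketed products in LTFU, and Protocol 4.1.2 restricts rescue ETV to extreme ALT elevations in children without access to an acceptable alternative.

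Table (3) raises a second issue. Its columns are the original study regimens, and regimens with different therapy mixes in LTFU would differ through collection alone.

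**Working it through.** The plan states no follow-up AE rate or cohort size, so there is no figure to reproduce. The check sets rules against denominators, then shows how the effect scales.

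**Step 1. Collection rule by therapy in LTFU**

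| Therapy | Non-serious AEs required | SAEs |
|---|---|---|
| Rescue ETV | All, at each visit | All |
| None | Those related to giving or stopping study drug; Week 6 recording | All |
| Commercial anti-HBV | Week 6 recording only | All |

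Protocol 7.4 (clinically significant laboratory results) and 7.7 (significant worsening on examination) add some capture in every row. The Week 6 recording falls inside the table (2) period only if commercial ETV has started by then.

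**Step 2. Rules mixed in each table**

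- Table (1), off-treatment follow-up, ends the day before any alternative therapy starts (SAP 6.1). It does not mix therapy groups, but beyond Week 6 it rests on drug-related non-serious AEs only.
- Table (2) mixes rows one and three. Concomitant ETV is in practice commercial, since Protocol 4.1.1 ends sponsor supply after the treatment phase except for rescue.
- Table (3) mixes all three rows.

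**Step 3. Direction and scale in table (2)**

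Let p be the percentage of children who would have at least one AE recorded under full collection (taken as equal in both groups), f the rescue share, and c the fraction of those AE cases still captured under the commercial rule. Then

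shown = p × [f + (1 − f) × c], and shortfall = p × (1 − f) × (1 − c).

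The shortfall is positive whenever f < 1 and c < 1. All inputs below are assumed; p = 60%.

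| f | shown, c = 0 | shown, c = 0.2 |
|---|---|---|
| 0.10 | 6% | 16.8% |
| 0.25 | 15% | 24% |
| 0.50 | 30% | 36% |
| 0.75 | 45% | 48% |

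For example, 60% × (0.25 + 0.75 × 0.2) = 60% × 0.40 = 24%. The ratio of shown to full, f + (1 − f) × c, does not depend on p. It runs from 0.10 (f = 0.10, c = 0) to 0.75 + 0.25 × 0.2 = 0.80 (f = 0.75, c = 0.2), and equals 1 if every child is on rescue.

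**Step 4. Table (3)**

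Suppose two regimens share the same p, and q is the percentage with an AE recorded among children not on rescue. A difference d in rescue share alone produces a gap of d × (p − q). With assumed p = 60% and q = 10%, d = 5 points gives 0.05 × 50 = 2.5 points, and d = 10 points gives 5 points.

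**Step 5. Time after rescue**

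Rescue lasts up to 96 weeks, with follow-up for at least 48 weeks afterwards (Protocol 4.1.2). After a full course, at least 48 of 96 + 48 = 144 weeks in the table (2) period fall outside the full-collection rule. SAP 8.9 derives a rescue start date but no end date, so this time cannot be separated as the SAP stands.

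**The case against.** Four points on the other side have force.

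- **Part of the remedy exists.** SAP 7.6.2 already summarises SAEs by regimen for all three follow-up cohorts, and table (1) already gives a largely off-therapy AE display. SAP 7.1 leaves table formats to a Data Presentation Plan that is not among the documents, so footnotes may be planned there. This stands and narrows the fix. A format document would not change the SAP's denominators.
- **Non-rescue children are not unobserved.** A reader might infer that non-serious AEs are simply not collected outside rescue. The documents do not support that. Untreated children have drug-related AEs documented, everyone has the Week 6 recording, and Protocol 7.4 and 7.7 add more. Collection is partial in untreated children and thin in commercial users.
- **The open-ended period does not lower the percentage.** A reader might count the time after rescue as further dilution. Extending the window can only add children with events, so a per-subject percentage cannot fall. What the open end does is make table (2) a summary from ETV restart onwards, rather than on ETV.
- **The tables are descriptive.** No test or confidence interval is planned for follow-up AEs, and the regimen columns overlap and depend partly on treatment after randomisation. Table (3) was never a clean comparison. This limits the harm without making the percentages readable as incidence.

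**Conclusion.** The concern holds for table (2). Whenever some alternative-ETV users are on commercial ETV, the All Grades percentage understates AE incidence after ETV restart. The direction follows from the collection rules and the denominator definition. The size is unknown, because the documents give no rescue counts, no follow-up AE rate and no capture fraction. The figures in the working illustrate scale and are not estimates; if most users are on rescue ETV, the effect is modest.

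Table (3) mixes full, partial and near-SAE-only collection. Its All Grades percentages should be read neither as incidence nor as a comparison between regimens.

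Two wider readings are not supported. One is that table (1) is free of the problem: it avoids mixing therapy groups, but its non-serious AEs beyond Week 6 are limited to study-drug-related events. The other is that the trial's safety conclusions are compromised generally: SAE, death, laboratory and on-treatment AE summaries are unaffected, and so is efficacy. This is a descriptive-table defect that is worth correcting because the correction is cheap.

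**What to change.** - **SAP 7.6.5, table (2):** split by ETV source. For rescue ETV, show all AEs from rescue start to rescue end plus 5 days, matching the SAP's on-treatment convention. For commercial ETV, show SAEs only. State how a child who takes both is handled, for example by assigning events to the source in use at onset.
- **SAP 8.9:** add a rescue end date, derived from the rescue ETV medication CRF that already supplies the start date.
- **Table (3):** state that regimens are compared on the SAE summary in SAP 7.6.2, not on All Grades AEs.
- **All follow-up AE tables:** footnote the collection rule. For table (1), say that non-serious AEs beyond Week 6 are limited to those related to giving or stopping study drug.

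The cost is a few sentences in two SAP sections, one derived date, one table split by a flag, and footnotes. Footnotes alone would warn the reader but leave table (2)'s denominator wrong.

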### **7.6.6 Clinical Laboratory Evaluations**

Summaries are based on subjects with at least 1 laboratory measurement during the study period.

#### **7.6.6.1 Laboratory Abnormalities**

For each laboratory test, laboratory abnormalities by toxicity grade (Grade 1 - 4; Grade 3 - 4) on treatment are summarized by treatment regimen and baseline status (all, normal, abnormal, not reported) for the following 3 cohorts:

- Through Week 48 on blinded therapy for treated subjects
- After Week 48 on blinded therapy or on open-label ETV through Week 96 for the Year 2 Safety Cohort
- On ETV treatment for All ETV Safety Cohort

Laboratory tests include:

- Hematology: hemoglobin, platelets, international normalized ratio (INR), white blood cell count (WBC) and neutrophils + bands (absolute)
- Liver function tests: alanine aminotransferase (ALT), aspartate aminotransferase (AST), total bilirubin and albumin
- Pancreatic enzymes: lipase (colorimetric or turbidimetric assay)
- Renal function tests: creatinine and BUN/urea (BUN or urea)
- Electrolytes (low and high): chloride, potassium and sodium.

Toxicity grades are based on DAIDS, unless specified otherwise (see Protocol Appendix 2). BUN/urea and chloride are graded with modified WHO criteria.

Treatment emergent laboratory abnormalities by toxicity grade (increased to Grades 1, 2, 3 and 4) are also summarized analogously by treatment regimen and baseline status for the 3 cohorts. On-treatment emergent abnormalities are those with a higher toxicity grade than the baseline toxicity grade (including not reported baseline).

In addition, the following select laboratory elevations and abnormalities on treatment are summarized by treatment regimen for the 3 cohorts:

- Any Grade 3 - 4 laboratory abnormality (see previous list of tests)
- Liver function elevations  $> 2$  and  $> 3$  x baseline (ALT, AST, total bilirubin)
- Liver function elevations  $> 2$  x baseline and Grade 4 (ALT, AST and total bilirubin; includes ALT flares, defined as ALT  $> 2$  x baseline and  $> 10$  x ULN)
- Simultaneous ALT and total bilirubin elevations (ALT  $> 2$  x baseline, total bilirubin  $> 2$  x baseline and  $> 2$  x ULN; ie, those occurring on the same collection day).

- Albumin < 2.5 g/dL
- Lipase elevations > 3 x baseline
- Confirmed creatinine elevations  $\geq 0.3$  and  $\geq 0.5$  mg/mL from baseline (2 sequential measurement or last measurement meeting the elevation criteria)
- Glucose categories (< 50,  $\geq 200$  mg/dL) regardless of fasting status.

For PBO-treated subjects who receive open-label ETV, baseline is used during blinded dosing, while ETV baseline is used during open-label ETV dosing.

Laboratory abnormalities by toxicity grade (Grade 1 - 4; Grade 3 - 4) are also summarized by treatment regimen and EOD status (all, normal, abnormal) for the first 2 follow-up cohorts: (1) off-treatment follow-up for off-treatment follow-up subjects in the Post-Year 1 Safety Cohort; (2) long-term follow-up for long-term follow-up subjects in the Post-Year 1 Safety Cohort.

Laboratory abnormalities by toxicity grade (Grade 1 - 4; Grade 3 - 4) are also summarized by treatment regimen during alternative ETV follow-up for alternative ETV follow-up subjects in the Post-Year 1 Safety Cohort.

Emergent laboratory abnormalities by toxicity grade (increased to Grades 1, 2, 3 and 4) are also summarized analogously by treatment regimen and EOD status for the first 2 follow-up cohorts. Emergent abnormalities are those with a higher toxicity grade than the EOD toxicity grade.

Select laboratory elevations and abnormalities are summarized relative to the EOD value for the 3 follow-up cohorts. In addition, elevations of liver function tests (including ALT flares, defined as ALT > 2 x reference and > 10 x ULN) during the follow-up periods are summarized using the reference value (REF) (ie, minimum of the baseline and EOD values) for the 3 follow-up cohorts. Note that for PBO-treated subjects who receive open-label ETV, reference is the minimum of the ETV baseline and EOD values.

ALT multiples of ULN and HBV DNA values are plotted over time for each subject who had an ALT flare on study. The duration of an ALT flare is measured from the first ALT measurement meeting the ALT flare criteria to resolution, defined as (1) the first ALT  $\leq$  baseline or  $\leq 5$  x ULN on treatment, or (2) the first ALT  $\leq$  reference or  $\leq 5$  x ULN during follow-up. If (1) and (2) are not met, an ALT flare is considered unresolved, and the last ALT measurement is used to estimate duration.

The time to and duration of ALT flares (weeks) during off-treatment follow-up are summarized for off-treatment follow-up subjects in the Post-Year 1 Safety Cohort (limited to ETV, PBO OL, and All ETV). Analyses are based on the first ALT flare during off-treatment follow-up.

The laboratory value during the study period with the highest toxicity grade is reported for each test. Grade 1 abnormalities are reset to normal if the original (unconverted) values are between the lower and upper limits of normal.

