5.3.1 Dose Modifications

ETV is a nucleoside analogue that is primarily cleared by the kidneys. In patients with renal impairment, the apparent clearance of entecavir decreases as creatinine clearance decreases. In the unlikely event that a subject develops inadequate renal function while on study (estimated glomerular filtration rate of $< 50 \text{ mL/min/1.73 m}^2$), the recommendation for dose reduction will follow the established approach used in studies of adult CHB patients. [Table 5.3.1](#) shows the recommendation for dose reduction based upon estimated glomerular filtration rate (GFR).

Table 5.3.1: Recommended Dosing of ETV in Subjects Who Develop Renal Impairment on Study

Estimated GFR	Usual Dose (0.015 mg/kg/day up to a maximum of 0.5 mg/daily) ^a
≥ 50	Usual Dose
30 to < 50	Dose reduction by 50 % OR Usual dose every 48 hours
10 to < 30	Dose reduction by 70 % OR Usual dose every 72 hours
< 10/hemodialysis/ CAPD ^b	Dose reduction by 90 % OR Usual dose every 7 days

^a For doses less than 0.5 mg daily, the oral solution is recommended.

[figure not shown]
^b Subjects receiving ETV on the day of hemodialysis should receive ETV after the session.

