6 STUDY ASSESSMENTS AND PROCEDURES

6.1 Flow Chart/Time and Events Schedule

Table 6.1: Flow Chart for Protocol AI463189

Procedure	Screening ≤ 6 Weeks prior to Randomization	Randomize Initiate study drug (Day 1) within 72 hours	On Study Treatment Weeks 4, 8, 12 ± 3 days, and every 12 weeks ± 5 days up to end of study drug dosing	Weeks 52, 100 and 148 ± 10 days (if needed) ^a	End of Treatment (Scheduled or Early)	Observational LTFU ^b Weeks 6, 12, and every 12 weeks ± 5 days Up to 264 weeks total study participation [or 48 weeks beyond completion of rescue open- label ETV used for treatment of an extreme elevation of ALT due to acute exacerbation of CHB; whichever is later]	Protocol Section
Eligibility Assessments							
Informed Consent	X						3.3
Inclusion/Exclusion Criteria	X						4.2
Medical & anti HBV history ^c	X						4.2
HCV, HDV serology (1 mL)	X						6.9
Alpha Fetoprotein (1 mL)	X						6.9

Table 6.1: Flow Chart for Protocol AI463189

Procedure	Screening ≤ 6 Weeks prior to Randomization	Randomize Initiate study drug (Day 1) within 72 hours	On Study Treatment Weeks 4, 8, 12 ± 3 days, and every 12 weeks ± 5 days up to end of study drug dosing	Weeks 52, 100 and 148 ± 10 days (if needed) ^a	End of Treatment (Scheduled or Early)	Observational LTFU ^b Weeks 6, 12, and every 12 weeks ± 5 days Up to 264 weeks total study participation [or 48 weeks beyond completion of rescue open- label ETV used for treatment of an extreme elevation of ALT due to acute exacerbation of CHB; whichever is later]	Protocol Section
Safety Assessments							
Physical Examination	X				X		6.3
Targeted Physical Examination (including neurologic assessment)		X	X			X ^d	6.3
Vital Signs including height, and weight	X	X	X		X	X	6.3
Tanner Stage Assessment		X	Week 24 and every 24 weeks		X	Week 24 and every 24 weeks	App 3
Pretreatment Events Assessment		X					6.3
Adverse Events Assessment			X		X	X ^e	6.3

Table 6.1: Flow Chart for Protocol AI463189

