**DIVISION OF AIDS TABLE FOR GRADING THE SEVERITY OF
ADULT AND PEDIATRIC ADVERSE EVENTS
PUBLISH DATE: DECEMBER, 2004**

LABORATORY				
PARAMETER	GRADE 1 MILD	GRADE 2 MODERATE	GRADE 3 SEVERE	GRADE 4 POTENTIALLY LIFE-THREATENING
Infant [†] , ≤ 14 days (non-hemolytic)	NA	20.0 – 25.0 mg/dL 342 – 428 μmol/L	25.1 – 30.0 mg/dL 429 – 513 μmol/L	> 30.0 mg/dL > 513.0 μmol/L
Infant [†] , ≤ 14 days (hemolytic)	NA	NA	20.0 – 25.0 mg/dL 342 – 428 μmol/L	> 25.0 mg/dL > 428 μmol/L
Calcium, serum, high (corrected for albumin)				
Adult and Pediatric ≥ 7 days	10.6 – 11.5 mg/dL 2.65 – 2.88 mmol/L	11.6 – 12.5 mg/dL 2.89 – 3.13 mmol/L	12.6 – 13.5 mg/dL 3.14 – 3.38 mmol/L	> 13.5 mg/dL > 3.38 mmol/L
Infant [†] , < 7 days	11.5 – 12.4 mg/dL 2.88 – 3.10 mmol/L	12.5 – 12.9 mg/dL 3.11 – 3.23 mmol/L	13.0 – 13.5 mg/dL 3.245 – 3.38 mmol/L	> 13.5 mg/dL > 3.38 mmol/L
Calcium, serum, low (corrected for albumin)				
Adult and Pediatric ≥ 7 days	7.8 – 8.4 mg/dL 1.95 – 2.10 mmol/L	7.0 – 7.7 mg/dL 1.75 – 1.94 mmol/L	6.1 – 6.9 mg/dL 1.53 – 1.74 mmol/L	< 6.1 mg/dL < 1.53 mmol/L
Infant [†] , < 7 days	6.5 – 7.5 mg/dL 1.63 – 1.88 mmol/L	6.0 – 6.4 mg/dL 1.50 – 1.62 mmol/L	5.50 – 5.90 mg/dL 1.38 – 1.51 mmol/L	< 5.50 mg/dL < 1.38 mmol/L
Cardiac troponin I (cTnI)	NA	NA	NA	Levels consistent with myocardial infarction or unstable angina as defined by the manufacturer
Cardiac troponin T (cTnT)	NA	NA	NA	≥ 0.20 ng/mL OR Levels consistent with myocardial infarction or unstable angina as defined by the manufacturer
Cholesterol (fasting)				
Adult ≥ 18 years	200 – 239 mg/dL 5.18 – 6.19 mmol/L	240 – 300 mg/dL 6.20 – 7.77 mmol/L	> 300 mg/dL > 7.77 mmol/L	NA
Pediatric < 18 years	170 – 199 mg/dL 4.40 – 5.15 mmol/L	200 – 300 mg/dL 5.16 – 7.77 mmol/L	> 300 mg/dL > 7.77 mmol/L	NA
Creatine Kinase	3.0 – 5.9 x ULN [‡]	6.0 – 9.9 x ULN [‡]	10.0 – 19.9 x ULN [‡]	≥ 20.0 x ULN [‡]
Creatinine	1.1 – 1.3 x ULN [‡]	1.4 – 1.8 x ULN [‡]	1.9 – 3.4 x ULN [‡]	≥ 3.5 x ULN [‡]
Glucose, serum, high				
Nonfasting	116 – 160 mg/dL 6.44 – 8.88 mmol/L	161 – 250 mg/dL 8.89 – 13.88 mmol/L	251 – 500 mg/dL 13.89 – 27.75 mmol/L	> 500 mg/dL > 27.75 mmol/L
Fasting	110 – 125 mg/dL 6.11 – 6.94 mmol/L	126 – 250 mg/dL 6.95 – 13.88 mmol/L	251 – 500 mg/dL 13.89 – 27.75 mmol/L	> 500 mg/dL > 27.75 mmol/L

^{*} Values are for term infants.

[‡] Use age and sex appropriate values (e.g., bilirubin), including preterm infants.

**DIVISION OF AIDS TABLE FOR GRADING THE SEVERITY OF
ADULT AND PEDIATRIC ADVERSE EVENTS
PUBLISH DATE: DECEMBER, 2004**

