### **7.3.4 Demographic and Other Baseline Characteristics**

Summaries are presented by as-treated treatment regimen for treated subjects unless specified otherwise. Summaries identify the number and percent of subjects with not reported (i.e., missing) measurements, unless specified otherwise.

If  $\geq 5\%$  of treated subjects have as-randomized regimen different than as-treated regimen, then demographics and baseline disease HBV characteristics are summarized analogously by as-randomized treatment regimen for treated subjects.

Demographic and other baseline characteristics are summarized by treatment regimen and overall for treated subjects:

- Demographics: age (years), age randomization strata ( $\geq 2$  to  $\leq 6$ ,  $> 6$  to  $\leq 12$ ,  $> 12$  to  $< 18$  years), gender, race, ethnicity, geographic region (Asia, Europe, North America, South America), country
- HBV disease characteristics: HBV DNA ( $\log_{10}$  IU/mL), Hepatitis B Surface Antigen (positive, negative, indeterminate), Hepatitis B E Antigen (positive, negative, indeterminate), Hepatitis B E Antibody (positive, negative, indeterminate), HBV genotype (e.g., A, B, C, D, E, indeterminate), INR, albumin (g/dL), ALT (U/L), ALT categories ( $\leq 2 \times$  ULN,  $> 2 \times$  ULN), total bilirubin (mg/dL), creatinine (mg/dL), glomerular filtration rate ( $< 50$ ,  $50 - 75$ ,  $> 75$  mL/min/1.73 m^2) estimated with Schwartz's formula, route of transmission (mother-to-

- child transmission; household/close contact exposure; transfusion; sexual contact; IV drug use; other)
- Physical measurements: height (cm), height for age Z score (HAZ), height for age percentile (HAP), weight (kg), weight for age Z score (WAZ), weight for age percentile (WAP), body mass index (BMI;  $\text{kg}/\text{m}^2$ ), BMI for age Z score (BMIAZ), BMI for age percentile (BMIAP) (see [Section 7.6.7](#))
  - Laboratory tests (see [Section 7.6.6.1](#))
    - Hematology by toxicity grade (ie, normal, Grade 1, 2, 3, 4)
    - Liver function tests by toxicity grade
    - Pancreatic enzymes by toxicity grade
    - Renal function tests by toxicity grade
    - Electrolytes (low and high) by toxicity grade
    - Glucose categories regardless of fasting status
  - Medical history by body system
  - Prior medications, defined as non-study medications taken before the first dose of study therapy.

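### The SAP does not analyse eGFR after baseline, so the report cannot count subjects who fall below the protocol's on-study renal threshold (eGFR < 50), and the fixed creatinine-rise criterion is least sensitive in the smallest children

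*SAP*

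**What the plan says.** Protocol 5.3.1 describes ETV as mainly renally cleared. The paragraph opening "In the unlikely event that a subject develops inadequate renal function while on study" defines that state as eGFR < 50 mL/min/1.73 m², and Table 5.3.1 is banded on eGFR. Exclusion 4c (protocol 4.2.2) uses the same limit and gives the Schwartz form, k × height / creatinine, without a value for k.

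The SAP uses eGFR in two places:
- the baseline description in 7.3.4, which lists "total bilirubin (mg/dL), creatinine (mg/dL), glomerular filtration rate" in the categories < 50, 50 to 75 and > 75;
- the screening deviation for exclusion 4c in Appendix 1.

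After baseline, SAP 7.6.6.1 lists "Renal function tests: creatinine and BUN/urea (BUN or urea". It also counts creatinine rises of at least 0.3 and 0.5 "from baseline (2 sequential measurement or last measurement meeting the elevation criteria". On grading it says "Toxicity grades are based on DAIDS, unless specified otherwise (see Protocol Appendix 2". The DAIDS creatinine grades are multiples of ULN, and their footnote reads "Use age and sex appropriate values (e.g., bilirubin), including preterm infants". SAP 7.6.6.2 summarises creatinine values by visit. SAP 7.6.8 repeats the grades and selected elevations by age stratum, on blinded therapy through Week 48. None of these sections, nor the on-treatment deviations in Appendix 1, mentions eGFR.

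Table 6.1 of the protocol schedules "Vital Signs including height, and weight" and chemistry at baseline, on-treatment, end-of-treatment and follow-up visits. Creatinine is in the chemistry panel (protocol 6.9.1).

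**The concern.** The protocol judges renal function on a size-corrected scale, at entry and on study, whereas the SAP reports it after baseline only through creatinine and BUN/urea. Two consequences follow. First, no planned table gives the number of children who fell below the protocol's own limit. Second, a fixed absolute rise stands for very different losses of function in a two-year-old and a seventeen-year-old, because creatinine depends on body size. Long-term paediatric safety is a stated secondary objective (protocol 2.2), and subjects are followed for five years while they grow.

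**Working it through.** The plan states no figure to reproduce. The check uses the protocol's formula, eGFR = k × Ht / Cr.

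**Inputs from the documents:** threshold 50; rise criteria 0.3 and 0.5; DAIDS creatinine Grade 1 at 1.1 to 1.3, Grade 2 at 1.4 to 1.8 and Grade 3 at 1.9 to 3.4 × ULN; ages 2 to < 18 years.

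**Assumptions (not in the documents):** k 0.413 to 0.55; height 90 to 170 cm, with 87 cm for a child of about two; creatinine 0.2 to 1.0 mg/dL; toddler ULN 0.4 to 0.6 mg/dL. The rise criteria are read as mg/dL. The SAP prints "mg/mL from baseline (2 sequential measurement or last measurement meeting the elevation criteria" although 7.3.4 gives creatinine in mg/dL; that is a separate point to reconcile.

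**1. eGFR fall implied by a fixed rise d.** At unchanged height the fall is d / (Cr0 + d), and k cancels.

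| Cr0 (mg/dL) | fall at +0.3 | fall at +0.5 |
|---|---|---|
| 0.2 | 60% | 71% |
| 0.3 | 50% | 62.5% |
| 0.5 | 37.5% | 50% |
| 0.8 | 27% | 38% |
| 1.0 | 23% | 33% |

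A child going from 0.30 to 0.59 loses 1 − 0.30/0.59 = 49% and stays below the 0.3 criterion.

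**2. Rise needed to reach eGFR 50 from a starting value g.** Rise = k × Ht × (1/50 − 1/g).
- g = 55: 0.413 × 90 × 0.001818 = 0.07, up to 0.55 × 170 × 0.001818 = 0.17.
- g = 60: 0.413 × 90 × 0.003333 = 0.12, up to 0.55 × 170 × 0.003333 = 0.31.

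From 60 the rise reaches 0.3 only when k × Ht is at least 90, that is, above about 164 cm with k = 0.55. Below that, such crossings do not meet the criterion.

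**3. Crossing from a normal baseline.** Take an 87 cm child with Cr0 0.3.
- k = 0.413: creatinine at eGFR 50 is 0.413 × 87 / 50 = 0.72, a rise of 0.42.
- k = 0.55: 0.55 × 87 / 50 = 0.96, a rise of 0.66.

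Both meet the 0.3 criterion. With ULN 0.4 to 0.6 they are 1.2 to 1.8 × ULN (Grade 1 to 2) and 1.6 to 2.4 × ULN (Grade 2 to 3).

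**4. What grading does for a crossing from 60.** For the same child with k = 0.413, creatinine goes from 0.60 to 0.72. With ULN 0.6 that is 1.0 to 1.2 × ULN (normal to Grade 1). With ULN 0.5 it is 1.2 to 1.44 (Grade 1 to 2). With ULN 0.4 it is 1.5 to 1.8 (Grade 2 throughout, so no emergent grade). The grade may or may not move, and it does not identify eGFR < 50.

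**5. Growth at constant eGFR.** Creatinine then rises in proportion to height. Assume 6 cm/year from 130 cm and creatinine 0.6. Over 144 weeks (about 16.6 cm) the rise is 0.6 × 16.6/130 = 0.08. If k also moved from 0.55 to 0.70, it would be 0.6 × (146.6/130) × (0.70/0.55) − 0.6 = 0.26. Neither reaches 0.3.

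**The case against.** The strongest reply is that no commitment is broken. Protocol 8.4.2 promises laboratory abnormalities by DAIDS or WHO grade, and the SAP delivers that. Protocol 8.3 names no eGFR endpoint, and in 5.3.1 eGFR serves dosing in an event called unlikely. (SAP 4.4 is blacked out and cannot be judged.) This stands: the point is a gap in reporting, not a contradiction.

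A reader might infer more, in three ways that the documents do not support.
- **That renal safety rests on raw creatinine and fixed rises alone.** Creatinine is graded in ULN multiples with an age- and sex-appropriate footnote, BUN/urea is graded, and treatment-emergent grades are planned.
- **That falls below eGFR 50 go unreported.** From a normal baseline they would usually show as a rise or a grade (step 3). The crossings that escape the rise criterion start close to the limit and are modest falls: 1 − 50/55 = 9% and 1 − 50/60 = 17%.
- **That growth would be counted as renal change.** The computed growth rises stay below 0.3. No on-treatment change runs over 192 weeks from one baseline: ETV-arm dosing ends by Week 144, and placebo subjects are re-baselined at the start of open-label ETV (SAP 7.6.6.1). Through Week 48, randomisation stratified by age also balances growth between arms.

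Other routes exist but are indirect. Protocol 7.4 captures clinically significant results and those leading to interruption, discontinuation or corrective therapy as adverse events. SAP 8.10 carries dose reduction as an action taken, and SAP 7.4.1 summarises average daily dose. None yields a count on the eGFR scale. The laboratory alert table in protocol 5.3.2.2 has no renal row. In follow-up, creatinine elevations are measured from the end-of-dosing value, so an on-treatment rise becomes part of the reference.

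**Conclusion.** The point holds as a reporting gap of moderate importance. As planned, the report cannot state how many subjects crossed eGFR 50, because a creatinine grade or rise is not that count. The 0.3 criterion is about half as sensitive to relative loss at creatinine 0.3 as at 1.0 (50% against 23%), and most crossings from a starting eGFR of 55 to 60 fall short of it. Growth does not trigger the criterion in the scenarios computed, but it mixes with renal change in the creatinine values summarised by visit. The 50% and 23% figures depend only on the formula, unchanged height and the mg/dL reading. The crossing and growth figures also depend on the assumed k, heights, creatinine levels and growth rate. The reassurance about grading depends on the laboratory applying an age-appropriate ULN: against an assumed adult ULN of 1.2, eGFR 50 in the 87 cm child would be 0.6 to 0.8 × ULN and would be graded normal. The primary efficacy analysis is not affected.

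**What to change.** In SAP 7.6.6.1 and 7.6.6.2, derive Schwartz eGFR at every visit that has both creatinine and height, using the baseline formula and stating k. If k varies with age or sex, say how a change of k during the study is handled, since it can produce an artificial step. For the on-treatment and follow-up cohorts, and by age stratum, report:
- eGFR and percentage change over time;
- shifts across the SAP's own categories (< 50, 50 to 75, > 75);
- the number with confirmed eGFR < 50, using the confirmation rule the section already applies to creatinine;
- the number with confirmed percentage falls, at cut-points fixed in advance (the documents give none).

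Keep the creatinine and BUN/urea summaries, and state that the creatinine ULN used for grading is age- and sex-specific.

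The cost is SAP wording, one derived variable and a few supportive tables. No new data are needed. The downside is dependence on the chosen k. This changes reporting only and proposes no dose or clinical rule.
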